#### **4.2.1.5 Sensitivity analyses of the Primary Endpoint**

The majority of the sensitivity, and supplementary, analyses will be performed by means of replicating the main analysis using different censoring rules and different event definitions. For all such analyses, no KM plots of the CDFs will be produced, but the KM estimates for the two treatment arms evaluated at particular timepoints will be included in the tabular presentation.

#### **Undetermined cause of death**

Deaths adjudicated as ‘undetermined’ cause will be included in the composite endpoint, along with the components used for the main analysis of the primary endpoint. The Cox regression analysis as described in Section 4.2.1.4 will then be replicated using this endpoint.

### Events occurring post SED

The main analysis will be replicated using the entire follow-up time available for a patient, i.e. including events occurring post SED.

#### 4.2.1.6 Supplementary Analyses of the Primary Endpoint

##### Non-SCD events

All the deaths will be included in the composite endpoint along with the rest of the components, used for the main analysis of the primary endpoint. The Cox regression analysis as described in Section 4.2.1.5 will be replicated using this endpoint.

##### Drop-in

The sensitivity of the results observed in the main analysis to the “drop-in”, i.e. instances of patients starting on non-protocolized SZC, will be examined. This will be done by censoring such patients at the time of drop-in, correspondingly ignoring events that occur after the fact, and replicating the main analysis using the resulting time to event / censoring.

##### Assumption of proportional hazards for Cox model

The underlying assumption of proportional hazards for Cox model will be assessed. The assessments will include: visual examination of the negative logarithms of the KM curves, with a crossing of the curves indicating that the assumption is not met, and by introducing, and testing, the significance of a time-dependent covariate in the Cox regression model, with a significant interaction indicating that the assumption is not met. This will be done for the main analysis of the primary endpoint only.

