### **3.3 Sample Size Determination**

The study is event-driven. The primary objective of the study is to evaluate the efficacy of SZC versus placebo in reducing the incidence of the primary composite endpoint.

Assuming the true HR for SZC versus placebo is 0.8, 730 primary endpoint events will result in 84.7% statistical power to demonstrate a statistically significant difference at either second interim analysis using two-sided significance level of 1.64% or at the final analysis using two-sided significance level of 4.46%. Based on an assumption that the event rate of the primary composite endpoint is approximately 0.11 per patient-year in the placebo group, it is expected that approximately 2800 participants will need to be randomized. The anticipated recruitment period is planned to be 32 months. The anticipated average treatment period is approximately 37 months, which in practice will be dependent on the actual event rate observed during the study, as the study duration is event driven. Any decision to increase or decrease participant numbers will be based on blinded event rate data (e.g., observed overall event rate), and study discontinuation rate.

Assuming a screen failure rate of 50%, approximately 5600 participants will be enrolled to achieve approximately 2800 participants randomly assigned (1:1) to study intervention (SZC or placebo).

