#### **4.2.1.4 Main Analysis of the Primary Endpoint**

The analysis of the primary composite endpoint will be based on a Cox regression model that includes the following factors/covariates: treatment group, geographic region. The Efron method for handling ties will be used.

The estimate of the HR corresponding to the difference between treatment arms, the corresponding 95% two-sided confidence interval (CI) as well as the two-sided p-value for the null hypothesis of no difference will be reported. If the p-value falls below the significance limit as specified in Section 4.2.3, the null hypothesis will be rejected.

The contribution of each component of the primary composite endpoint to the overall treatment effect will be assessed. In the analysis of the components, all first events of the given type will be included, irrespective of any preceding non-fatal component of a different type. Each component in the composite endpoint will be analysed similarly to the composite primary endpoint, i.e. by means of a Cox regression.

Kaplan-Meier estimates will be calculated and plotted, both for the composite endpoint and for individual components. The KM estimate at 12, 24 and 36 months will be included in the tabular presentation of the primary endpoint analysis.

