#### **4.2.3 Multiplicity/Multiple Comparisons**

Testing for efficacy will be performed at two time points, first at 0.7 information fraction and at the final analysis. The significance levels for the interim and the final analyses will be adjusted to control the overall type I error rate at two-sided 5%. At the efficacy interim analysis, the hypothesis for the primary endpoint will be tested at two-sided 1.64% significance level (O'Brian and Fleming method implemented by East 6.5, Copyright © 2018 Cytel Inc.). If the outcome of the interim analysis is to stop the trial for efficacy, then the interim analysis results will be considered as the primary efficacy results. However, a supplementary analysis will be performed with the additional data up to the study termination.

If the trial does not stop at any interim, then the final analysis planned at 730 adjudicated events, will be performed at a two-sided significance level of 4.46%. If the actual information fraction at the efficacy interim look deviates from 0.70, the significance level

for the final analysis will be adjusted based on the actual number of adjudicated primary events at the interim and final analyses.

To control the familywise Type I error rate, a fixed sequence multiple testing procedure for primary and secondary endpoints will be performed.

For the primary endpoint, the following hypothesis will be tested:

$H_0: HR[\text{SZC:placebo}] = 1$

Versus

$H_1: HR[\text{SZC:placebo}] \neq 1$

If study is terminated early prior to conducting efficacy and futility interim analyses and for reasons unrelated to efficacy, primary endpoint will be tested at 5% two-sided significance level.

Once the null hypothesis concerning the primary efficacy endpoint is rejected, the hypotheses for the secondary efficacy endpoints will be tested separately in the order listed in Table 2, with the same alpha level as the primary endpoint. The testing procedure will continue down the hierarchy if the current endpoint is rejected and will stop if the current endpoint is not rejected.

No multiplicity correction will be applied to the family of exploratory analyses. Hence, the results obtained from these should be regarded as hypothesis generating, rather than confirmatory.

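### The SAP reads a crossing of the -log(KM) curves as failure of proportional hazards, but at the design effect such crossings are mostly chance and will often contradict the covariate test beside them

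*SAP*

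**What the plan says.** The primary analysis (SAP 4.2.1.4) is a "Cox regression model that includes the following factors/covariates: treatment group, geographic region", and the hazard ratio is the only population-level summary listed for the primary objective (SAP Table 1).

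SAP 4.2.1.6, under the heading on proportional hazards, names two assessments:

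- inspection by eye of the -log(KM) curves, "with a crossing of the curves indicating that the assumption is not met"
- "testing, the significance of a time-dependent covariate in the Cox regression model, with a significant interaction indicating that the assumption is not met"

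On scope it adds: "This will be done for the main analysis of the primary endpoint only".

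Four things are not stated: a time window, at-risk limit or minimum size for a crossing; the time function and significance level of the time-dependent term; which criterion prevails if they disagree; and what follows if the assumption is judged not met.

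**The concern.** The negative log of the Kaplan-Meier curve estimates the cumulative hazard. Under proportional hazards the two true cumulative hazards never cross unless the hazard ratio is 1. The estimated curves, however, both start at zero and are close together for months, so sampling error alone will make them change order. The -log transform is monotone, so the rule amounts to asking whether the Kaplan-Meier curves cross.

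The hazard ratio is the headline result and the Kaplan-Meier curves will be plotted. A harmless early crossing would let a reader cite the SAP's own words against a valid hazard ratio, while the covariate test in the same sentence shows no problem. With no rule for disagreement, the matter would be settled after the data are seen.

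**Working it through.** **Inputs from the documents.** Hazard ratio 0.8, 730 events, placebo rate 0.11 per patient-year, 2800 participants 1:1, 32 months of recruitment (SAP 3.3). Efficacy is tested "first at 0.7 information fraction and at the final analysis" (SAP 4.2.3).

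**Assumptions.** The documents give no censoring rates. Non-SCD death is taken as 0.10 per year (range 0.05 to 0.15) and other dropout as 0.02 per year. The covariate test uses treatment by log(time) or by time at two-sided 5%. The region covariate is omitted.

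**Step 1: reproduce the plan's own figure.** SAP 3.3 says: "Assuming the true HR for SZC versus placebo is 0.8, 730 primary endpoint events will result in 84.7% statistical power", the levels being "second interim analysis using two-sided significance level of 1.64% or at the final analysis using two-sided significance level of 4.46"%. The drift is √(730/4) × |ln 0.8| = 13.509 × 0.2231 = 3.0145. The final look alone at 4.46% (critical value 2.008) gives Φ(3.0145 − 2.008) = 84.3%. The two-look calculation gives 84.8%, so the stated power is reproduced. The SAP gives no operating figure for the proportional-hazards check.

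**Step 2: hand check of chance crossing at HR 0.8.** Ignore depletion of the risk set. The difference in cumulative hazard then has mean 0.11 × (1 − 0.8) × t = 0.022t and variance (0.11 + 0.088)t/1400, with t in years. The standardised gap is z(t) = 0.022t / √(0.198t/1400) = 1.85√t. For a Brownian path with this drift, the probability of touching zero at any time after t is 2Φ(−z).

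| Counted from | Mean gap | SE | z | 2Φ(−z) |
|---|---|---|---|---|
| Month 1 | 0.0018 | 0.0034 | 0.53 | 59% |
| Month 3 | 0.0055 | 0.0059 | 0.92 | 35% |
| Month 6 | 0.0110 | 0.0084 | 1.31 | 19% |
| Month 12 | 0.0220 | 0.0119 | 1.85 | 6% |

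**Step 3: simulation under exact proportional hazards.** There were 2000 trials per scenario, each stopped at 730 events. A crossing is a sign change in the difference of the -log(KM) curves once both arms have an event. Windowed counts drop the last 5% of follow-up.

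| True HR | Any time | From month 3 | From month 6 | From month 12 |
|---|---|---|---|---|
| 0.7 | 74% | 14% | 5% | 0.7% |
| 0.8 | 83–86% | 33–37% | 20–23% | 9–11% |
| 0.9 | 95% | 71% | 62% | 50% |
| 1.0 | 99% | 90% | 86% | 79% |

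The range at HR 0.8 covers the assumed death rates. A separate simulation with 12% censoring per year gave 85% at any time, 57% from month 1, 24% from month 6 and 11% from month 12. The hand check agrees closely up to month 6. It is lower at month 12, as expected, because it ignores the shrinking risk set.

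**Step 4: the covariate test and the conflict.** Under exact proportional hazards at HR 0.8 the covariate test rejects in 4% to 5% of trials. In one run crossing at any time occurred in 85.1%, the log-time test rejected in 5.0%, and at least one flagged in 86.4%. Both flagged in 85.1 + 5.0 − 86.4 = 3.7%, so the criteria disagreed in 86.4 − 3.7 = 82.7%. With crossings counted only from month 6, both flagged in 20.8 + 5.0 − 23.8 = 2.0%, so they disagreed in 23.8 − 2.0 = 21.8%.

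**Step 5: fading effects whose true curves never cross.**

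| Scenario | Crossing, any time | From month 3 | From month 6 | Covariate test | Either (crossing from month 3) |
|---|---|---|---|---|---|
| HR 0.65 to 18 months, then 0.95 | 75–76% | 19% | 13% | 45–55% | 56% |
| HR 0.60 in year 1, then 1.0 | 79% | 37% | 34–35% | 63–71% | 81% |

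Read literally, the crossing rule flags both violations less often than it flags a correct model (83–86%).

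**The case against.** The strongest reply is that the plot is only half of the check. The covariate test is aimed at effects that fade without the curves crossing, and Step 5 shows that it does much of that work. A reader might infer that the SAP's check as a whole misses such effects, or that the model is passed when the curves do not cross. The documents support neither reading: the SAP names both assessments, and it never says that absence of a crossing shows the assumption to be met. Nor should fading be equated with no crossing, since estimated curves cross in 34% to 37% of trials in the second scenario when read from month 3 or 6.

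Second, the SAP calls for visual examination. A sensible reader would discount a tangle in the first weeks, when the expected cumulative hazards are about 0.009 and 0.007 on a plot that reaches 0.11 × 3 = 0.33 for placebo at month 36. That is fair, and it is why the windowed figures matter more than the 85%. But the SAP sets no window, and ignoring the first 6 months still leaves about one trial in five wrongly flagged.

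Third, some replacements are a matter of preference. Log(-log KM) curves cross at exactly the same times, parallelism is also judged by eye, and a scaled Schoenfeld test largely repeats the covariate test. This stands. The needed change is to drop crossing as a criterion; the choice of descriptive plot is secondary.

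**Conclusion.** The concern holds for the crossing criterion and for the missing rule on disagreement. At HR 0.8 under exact proportional hazards, the curves cross by chance in about 85% of trials at any time, about 20% to 25% after month 6 and about 10% after month 12. The smaller the true effect, the worse this gets: at HR 1.0 the figure after month 12 is 79% to 82% across simulations. The covariate test rejects falsely in about 5%, so the two criteria will often point in opposite directions.

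A reader might infer that a crossing puts the primary result at risk. It does not. The check is listed as supplementary, names no consequence, and leaves the primary model and significance levels as fixed in SAP 4.2.1.4 and 4.2.3. What is at stake is the interpretation of the hazard ratio, so this is a minor point worth correcting because it is cheap.

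The figures rest on assumed censoring rates, an assumed 5% test level and a model without region. Varying the assumed death rate from 0.05 to 0.15 per year moved the any-time figure only between 83% and 86%. The fading scenarios are illustrations, not predictions.

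**What to change.** In SAP 4.2.1.6:

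1. Delete the clause that treats a crossing as evidence against proportional hazards.
2. Keep a plot as description only, for example log(-log KM) curves viewed for parallelism, or scaled Schoenfeld residuals against time.
3. Let the treatment-by-time covariate test decide, and state its time function (for example log time) and its significance level.
4. State the consequence: if the term is significant, report hazard ratios by period (for example 0–12, 12–24 and over 24 months) beside the overall hazard ratio. The primary test is unchanged.

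The cost is a few sentences in the SAP and standard output, with no new data and no effect on type I error for the primary endpoint. At HR 0.8 it cuts false declarations of non-proportionality from about 85%, read literally, to about 5%. The test's sensitivity to the fading effects examined stays at 45% to 71%, so a non-significant result should not be reported as proof of proportionality.

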#### 4.2.1.7 Subgroup Analyses

The consistency of the treatment effect observed in the main analysis will be evaluated with respect to the following demographic/baseline characteristic and prognostic factors:

- Sex
- Age at baseline
  - categorization 1 (<65, 65 - 84, ≥ 85)
  - categorization 2 (<65, 65 - 74, ≥ 75)
  - categorization 3 (<65, ≥65)
- Race (White, Black or African American, Asian, American Indian or Alaska Native, Native Hawaiian or other Pacific Islander, Other, Not reported)
- Geographic Region (Asia, Europe, North America, South America)
- Region (USA, Non-USA)
- Baseline S-K (<5.5, 5.5-6.5, >6.5)
- BMI (<30, ≥ 30 kg/m^2)
- Ethnicity (Hispanic or Latino, Not Hispanic or Latino)
- Haemodialysis access type (Arteriovenous Fistula, Arteriovenous Graft, Tunnelled Catheter, Other)

- Historical arrhythmia (yes/no) at baseline.
- Prior History of
  - Atrial Fibrillation (Yes, No)
  - Ventricular Tachycardia (Yes, No)
  - Ventricular Fibrillation (Yes, No)
  - Stroke/TIA (Yes, No)

The Cox proportional hazards model used for the primary analysis (Section 4.2.1.4), including a factor for the relevant subgroup and the treatment-by-subgroup interaction, will be used for each subgroup analysis. HR for each level of the subgroup will be estimated separately.

The presentation of the results will include the estimate of the HR between treatment arms in the respective sub-group, the corresponding 95% CI and the p-value for the interaction term.

Results will also be plotted using a forest plot.

#### 4.2.2 Secondary and Exploratory Objectives

##### Potassium levels at 12 months visit

The primary analyses of potassium levels at 12 months will be based on the available data (i.e. no imputation performed).

##### Normokalemia

Two definitions of normokalemic will be used to assess the likelihood of a patient being normokalemic at the 12 months visit. For the purpose of analyzing the corresponding secondary objective, normokalemia will be defined as:

- S-K of 4.0-5.5 mmol/L (yes/no), as measured by the central lab, after the long interdialytic interval (LIDI).

For the purpose of analyzing the corresponding exploratory objective, normokalemia will be defined as:

- S-K of 4.0-5.0 mmol/L (yes/no), as measured by the central lab, after the long interdialytic interval (LIDI).

A logistic regression model with the binary variable (yes/no) as response and the same covariates as for the main analysis of the primary objective described in Section 4.2.1.4 will be used. The estimated odds ratio, corresponding 95% confidence interval, and two-sided p-value will be presented. The proportion of normokalemic subjects in each treatment arm

will also be presented, with the number of patients with available SK data in the respective treatment arms used as the denominator.

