#### **Type of Participant and Disease Characteristics**

- 4 Receiving hemodialysis (or hemodiafiltration) 3 times a week for treatment of ESRD for  $\geq$  4 months before enrollment

- 5 Must have hemodialysis access consisting of an arteriovenous fistula, arteriovenous graft, or tunneled (permanent) catheter which is expected to remain in place for the entire duration of the study
- 6 At least 2 out of 2 or 2 out of 3 pre-dialysis S-K values  $\geq 5.5$  mmol/L after the LIDI during screening

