#### **3.4.1.5 Others**

##### **Baseline value**

For both efficacy and safety analyses the baseline value for all variables is defined as the last value obtained during screening period on or prior to the date of randomization.

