### **Severe hyperkalemia**

Severe hyperkalemia will be defined as  $S\text{-}K > 6.5 \text{ mmol/L}$  (yes/no) after the LIDI. The same analysis as for the classification of potassium into normal / abnormal (i.e. a logistic regression) will be performed.

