### **Sensitivity Analysis**

To assess sensitivity of the result to missing data assumptions, binary endpoints based on potassium levels at the 12 months will be analysed using Full Analysis Set (all randomized subjects). Subjects with missing values will be considered as non-responders. For severe hyperkalemia endpoint ( $S\text{-}K > 6.5 \text{ mmol/L}$  (yes/no)), subjects with missing values will be considered as having severe hyperkalemia.

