### **Supplementary analyses**

The distribution of the SK values at the 12 months visit, as well as at baseline, in each treatment arm, will be illustrated by means of a box plot. A complimentary table presenting the summary statistics (mean, SD, median, min, max, quartiles) describing the distribution of SK, as well as the distribution of difference in SK as compared to baseline, per treatment arm, will also be provided.

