#### **4.5.2 Clinical Laboratory, Vital Signs and ECG**

Blood samples will be taken at Visit 1, 2, 3, 4 (randomization), and 8 (12-month) for the determination of clinical chemistry by a central laboratory; a full list of the laboratory variables for this study is provided in Table 7 of the CSP. For the definition of baseline, see Section 3.3.1.5.

Vital signs (pulse and BP) will be assessed at Visit 1, 4 (randomization) and end of study intervention visit (EOIV) or premature study intervention discontinuation visit (PIDV).

A 12-lead ECG will be performed at Visit 1 and 4 (randomization). That is, only the baseline ECG value will be available for this study.

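### The three 12-month serum potassium logistic models leave out baseline serum potassium and so give up a modest amount of test efficiency

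*SAP*

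**What the plan says.** SAP 4.2.1.4 bases the primary analysis on a "Cox regression model that includes the following factors/covariates: treatment group, geographic region". SAP 4.2.2 carries that covariate list into both normokalemia endpoints: "A logistic regression model with the binary variable (yes/no) as response and the same covariates as for the main analysis of the primary objective". For severe hyperkalemia it adds: "The same analysis as for the classification of potassium into normal / abnormal (i.e. a logistic regression) will be performed". None of the three models contains baseline S-K.

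The baseline measurement exists:

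- On central-laboratory chemistry, SAP 4.5.2 says: "Blood samples will be taken at Visit 1, 2, 3, 4 (randomization), and 8 (12-month" visit).
- SAP 3.4.1.5 fixes which value counts: "the baseline value for all variables is defined as the last value obtained during screening period on or prior to the date of randomization".
- Protocol 5.1 makes eligibility depend on the measurement: "At least 2 out of 2 or 2 out of 3 pre-dialysis S-K values" must be at least 5.5 mmol/L.

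The SAP uses baseline S-K as a descriptive characteristic (4.1.5), as a subgroup factor for the primary endpoint (4.2.1.7) and in the S-K summaries, where "the distribution of difference in SK as compared to baseline, per treatment arm, will also be provided". Protocol 9.4.2.2 allows further covariates in the logistic models; the SAP names none. The one sensitivity analysis of these endpoints concerns missing values: "binary endpoints based on potassium levels at the 12 months will be analysed using Full Analysis Set (all randomized subjects"), with missing counted as the unfavourable outcome.

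**The concern.** Each endpoint is a dichotomised 12-month potassium value, so the baseline value of the same variable is the natural prognostic covariate. Leaving out a prognostic covariate in logistic regression pulls the odds ratio towards 1 and lowers the expected test statistic.

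The ranking gives this some weight. Under SAP 4.2.3 testing stops at the first endpoint that is not rejected. S-K 4.0–5.5 stands first of nine secondaries, with eight below it. S-K > 6.5 stands fifth, with sudden cardiac death, stroke, cardiovascular death and all-cause death below it. Power lost on either endpoint can close the path to those below.

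**Working it through.** **The plan's own figure.** The documents give no power for the S-K endpoints. The stated power is for the primary endpoint: 84.7% with 730 events and HR 0.8 (SAP 3.3). The drift is √(730/4) × |ln 0.8| = 13.51 × 0.2231 = 3.01. With two looks at two-sided 1.64% and 4.46%, power is 84.8%, so the figure reproduces. It does not bear on the S-K models.

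**Inputs.** From the documents: 2800 randomised 1:1, and two-sided 4.46% at the final analysis (critical value 2.008). Assumed: 2240 participants with a 12-month value (80% of 2800), placebo 12-month mean 5.8 and SD 0.75 mmol/L, no region effect, and a baseline-to-12-month correlation of 0.1, 0.3 or 0.5. Each cell had 4,000 paired runs, with and without continuous baseline S-K.

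**Unadjusted model by hand (S-K 4.0–5.5).**

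- Placebo: Φ(−0.40) − Φ(−2.40) = 0.336.
- SZC with a shift of −0.128: Φ(−0.229) − Φ(−2.229) = 0.396.
- Odds ratio: (0.396/0.604)/(0.336/0.664) = 1.30.
- SE of the log odds ratio: √[1/(1120 × 0.336 × 0.664) + 1/(1120 × 0.396 × 0.604)] = 0.088, as simulated.

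**Effect of adjusting at correlation 0.5.** The odds ratio moves from 1.30 to 1.35 and the SE from 0.088 to 0.095.

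- z goes from 0.262/0.088 = 2.98 to 0.300/0.095 = 3.16.
- The efficiency ratio is (3.16/2.98)² = 1.12. With 1.29 as the unadjusted odds ratio it is 1.19, so two-decimal rounding matters here.
- Approximate power goes from Φ(2.98 − 2.008) = 83% to Φ(3.16 − 2.008) = 87–88%, close to the simulated gain of 4.7 points.

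The SE rises; z grows because the odds ratio moves further.

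**Efficiency over the range.** The gain in effective sample size is about 0–0.5%, 4–5% and 13–19% at correlations 0.1, 0.3 and 0.5. Of 2240 participants that is at most 2240 × 0.005 = 11, then 90–112, then 291–426. A second simulation with other assumed inputs (2000 participants, 12-month SD 0.8, shift 0.1 mmol/L) covered all three endpoints and gave 2–3%, 6–8% and 18–24% at correlations 0.2, 0.4 and 0.6.

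**Power gain in percentage points (SE 0.2–0.6).**

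| Endpoint | Unadjusted power | Corr. 0.1 | Corr. 0.3 | Corr. 0.5 |
|---|---|---|---|---|
| 4.0–5.5 | about 61% | +0.6 | +2.7 | +6.3 |
| 4.0–5.5 | about 82% | +0.3 | +1.8 | +4.7 |
| 4.0–5.5 | about 92% | +0.4 | +0.8 | +2.7 |
| > 6.5 | about 68% | – | +2.4 | +5.5 |
| > 6.5 | about 86% | – | +1.0 | +4.8 |
| > 6.5 | about 98% | – | +0.2 | +1.0 |

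The shifts behind these rows are small: −0.10, −0.128 and −0.15 mmol/L for 4.0–5.5, and −0.12, −0.15 and −0.20 for > 6.5.

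**A large effect.** At −0.30 mmol/L, 34% versus 48% are normokalemic and 18% versus 9% are above 6.5. At correlation 0.5, z for S-K 4.0–5.5 is ln 1.80/0.087 = 6.8 unadjusted and ln 1.96/0.094 = 7.2 adjusted. Power is 100% either way.

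**Type I error (nominal 4.46%, SE 0.3).** 3.5–4.6% without baseline S-K, 3.8–4.7% with it.

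**Plausible correlation.** Selecting on screening values of at least 5.5 weakens the correlation. Assumed visit-to-visit values of 0.3, 0.5 and 0.7 before selection become 0.22–0.23, 0.33–0.36 and 0.48–0.52 if the baseline is the randomisation-visit sample, or 0.15–0.17, 0.26–0.30 and 0.43–0.48 if it is the last screening sample. So 0.5 is towards the upper end.

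**The case against.** The strongest objection is that the gain appears where it is least likely to matter. Protocol 2.2 describes SZC as effective in hemodialysis patients, and Protocol 6.1.2 titrates to 4.0–5.0 mmol/L. The S-K endpoints are tested only after the primary is rejected, and Appendix E puts the hypothesised benefit down to reducing interdialytic hyperkalemia, not to a direct drug effect. A positive primary result with almost no S-K effect would be hard to explain. With a clear S-K effect, both models reject. This stands, and it keeps the point minor.

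Titration may also weaken the link between baseline and month 12 in the SZC arm. Halving that arm's correlation (0.5 placebo, 0.25 SZC) cut the simulated power gain from about 6 to about 3.5 points. This stands too. The protocol's wording on covariates is a permission, so the SAP breaks no rule by adding none.

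A reader might infer that adjustment would narrow the confidence interval for the odds ratio. It would not: at correlation 0.5 the 95% half-width on the log scale goes from 1.96 × 0.088 = 0.172 to 1.96 × 0.095 = 0.186. A reader might also infer, because randomisation is stratified by country (Protocol 6.3) and the models use region, that the primary Cox analysis is unsound or needs a country-stratified check. The documents do not support that. Region is derived from the stratification country (SAP 3.4.1.5), it is the covariate the protocol names, simulation shows no inflation of type I error, and an added sensitivity analysis would leave the primary test unchanged.

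**Conclusion.** The point holds as a low-cost improvement, not as an error. The three S-K models omit a prognostic covariate that is collected, defined and permitted. Type I error is controlled and no stated figure is wrong.

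The cost is about 0–0.5%, 4–5% or 13–19% in effective sample size at correlations 0.1, 0.3 and 0.5, and less if titration weakens the correlation under SZC. In power it is a few points if the S-K effect is of the order of −0.10 to −0.15 mmol/L, and nothing at −0.30. These are illustrations: the correlation, SD, shift and number with 12-month data are assumptions, because the documents supply none of them.

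**What to change.** Before unblinding, amend SAP 4.2.2 to add continuous baseline S-K, as defined in SAP 3.4.1.5, to the logistic models for S-K 4.0–5.5, S-K > 6.5 and exploratory S-K 4.0–5.0, and to their missing-data sensitivity analysis. State that the odds ratio is conditional on baseline S-K and region. Make clear whether the randomisation-visit sample can serve as the baseline, since the definition refers to the screening period.

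The cost is SAP wording only: Protocol 9.4.2.2 already permits the covariate, and eligibility requires screening S-K values, so few if any participants should lack one. The SAP should state the downside: the conditional odds ratio lies further from 1 (about 1.30 to 1.35 at correlation 0.5) and the SE of its logarithm is larger (0.088 to 0.095). If a measure less dependent on the covariate set is wanted, a standardised risk difference from the same model can be reported beside it; its variability is slightly reduced by the adjustment. The primary Cox model stays as planned.
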